1 STUDY DETAILS

1.1 Study Objectives

- A. Do the background variables differ between NR-RTX and R-GC or NR-GC?
- B. Does RTX lower the CAS of the non-steroid responsive TAO-patients (NR-RTX), in comparison to NR-C, that continued with iv GC, and R-GC?

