Does RTX lower the CAS of the non-steroid responsive TAO-patients (NR-RTX), in comparison to NR-C, that continued with iv GC, and R-GC? Do the background variables differ between NR-RTX and NR-GC or R-GC? And lastly, does the QoL differ between the R-GC and the NR-RTX at given measuring points?

Material and Methods

Study design

The RTX-study is a non-randomized prospective study that covers patients with moderate-severe TAO with indication for treatment with iv GC. For this study, a control group (NR-C) will be created.

Patients with TAO are evaluated at Department of Ophthalmology at Sahlgrenska University Hospital/ Mölndal's and are asked for participation if eligible. Variables collected at each visit Clinical Activity Score (CAS), Quality of Life (QoL) through ThyPRO self-assessment questionnaire, biochemical tests (fT4, fT3, TSH, TRAb, liver function tests, fasting blood glucose), blood pressure and waist. An oral glucose tolerance test (OGTT) is performed at 12, 18, and 46 weeks, and a short adrenocorticotrophic hormone (ACTH) test at 12 and 46 weeks. Dual-energy x-ray absorptiometry (DXA) of the spine is conducted at 0 and 18 weeks.

All patients in the RTX-study start the 12-week scheme of iv GC at baseline. After four weeks of treatment, an evaluation of the treatment outcome is made. If the patients have improved their CAS score by ≥ 2 points, they are classified as responders to iv GC (R-GC) and continue their 12-week iv GC scheme. The remainder of the patients are classified as non-responders to the treatment with iv GC and are switched to 1000 mg iv RTX in week 5 and 7, combined with a weekly oral dose of 12.5 – 15 mg MTX (NR-RTX). The RTX is administered at the department of Rheumatology at Sahlgrenska University Hospital. All included patients have thereafter follow-up visits at week 12, 18, 32, 46 and 68 weeks after baseline.

At week 18 and at all follow-up timepoints thereafter, patients in R-GC group are evaluated for possible relapse. If a patient in R-GC has a CAS ≥ 4 points and CAS has worsened by ≥ 2 points compared to the value measured in the prior evaluation time-point, the patient is

considered having a relapse. Patients with relapse are randomized to either treatment with RTX and MTX or with *per oral* GC and MTX.

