All patients included in the study are assessed according to study protocol, but if DON is developed, the affected patient is treated outside the study protocol in order to follow DON treatment regimen. The patients with DON still have the same evaluation time points as the other patients in the study, but they are excluded from the comparisons between groups after the occurrence of DON.

From the group of patients with moderate – severe TAO with indication for treatment with iv GC that do not meet inclusion/exclusion criteria for the RTX-study or declined participation, a control group (NR-C) of non-responders will be created. As they are not included in the RTX study, they continue with their 12 weeks scheme of iv GC treatment.

Data collected at the follow-up timepoints: QoL, safety data and information on adverse events.

Study population

Inclusion criteria for the RTX study: man or woman between 18-70 years old, TAO with 7-point score system of CAS ≥ 4 (less than 3 months old), euthyroid for at least 6 weeks.

Exclusion criteria for the RTX study were: DON, ulcerative corneal involvement, previous treatment with steroids for TAO (except for prophylaxis for TAO in connection with RAI), previous treatment with RTX, positive Hepatitis B or C serology, obtained a living vaccine within 4 weeks prior RTX+MTX to evaluation, history of recurrent significant infection or history of recurrent bacterial infections, assessment by the investigator that the patient may not attend to the protocol, current pregnancy or lactation, significant cardiac disease, including significant or uncontrolled arrhythmia, previous active tuberculosis, bone marrow depression with leukopenia, thrombocytopenia or significant anaemia, allergy to the active substance or any other substance in the medications or murine proteins, active, severe infections (such as tuberculosis, sepsis or opportunistic infections), patients with severe immunosuppression, severe cardiac failure or severe uncontrolled heart disease.

The TAO patients not included in the RTX-study will be identified using the diagnosis-related group (DRG) registry according to the 10th revision (ICD-10) in VGR. In DRG, a combination of different codes was used (TAO [H06.2], Graves' disease [E05.0] and iv infusion [DT016]).

Efficacy variables

In the study, both patients' eyes are evaluated regarding CAS and the score of and any improvement of the worst eye was used.

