1.4 Power Calculation

No power calculation was performed due to the lack of data from any similar study of RTX in GC non-responders

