2 STUDY VARIABLES

2.1 Baseline Variables

2.1.1 Demographics and Baseline Characteristics only available at baseline

- Age (years)
- Sex (man /woman = m/w)
- Smoking status (smoker/previous smoker/non-smoker)
- Previous treatment (operation/RAI/ATD)
- Current treatment (Levothyrocin/ATD)
- Time from diagnosis of GD (years)
- Duration of eye symptoms (months)

2.1.2 Laboratory/evaluation measurements only available at baseline:

- fT4 (pmol/L)
- fT3 (pmol/L)
- TSH (mIE/L)
- Exophthalmometry left (mm)
- Exophthalmometry right (mm)
- Subjective diplopia (non/intermittent/corrected with prism)

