2.3 Analysis Variables

2.3.1 Primary Variable

- Change of CAS (clinical activity score) between the observation timepoints and the previous timepoint: comparison between the treatment groups
- CAS: comparison between the treatment groups at the different timepoints

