3 STATISTICAL METHODOLOGY

Tests between groups will be made for the NR-RTX group and all of the other groups one at a time; R-GC and NR-C (where applicable).

For continuous variables Mann-Whitney U-test will be used for analyses between two groups. For dichotomous variables Fisher exact test will be used for test between two groups. For ordered categorical variables Mantel Haenszel Chi Square test will be used for test between two groups.

For all continuous variables Wilcoxon's Signed-Rank test will be used for within group analyses.

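### The non-randomised NR-RTX v NR-C comparison of CAS is unadjusted, although baseline variables that could confound it are collected

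*SAP*

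**What the plan says.** The Protocol (Study design) states that "The RTX-study is a non-randomized prospective study". NR-C is formed from patients with an indication for iv GC who "do not meet inclusion/exclusion criteria for the RTX-study or declined participation", and who stayed on steroids although they did not respond. The Protocol's Objectives make NR-RTX v NR-C the primary aim and put the comparison of background variables second.

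SAP 1.1 turns that second aim into objective A: "Do the background variables differ between NR-RTX and R-GC or NR-GC". (NR-GC is read here as NR-C, the label used in objective B and in section 3.) SAP 2.1.1 lists the background data, including three-level smoking status and duration of eye symptoms in months.

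SAP 2.3.1 gives as one primary variable "CAS: comparison between the treatment groups at the different timepoints"; the other is the change in CAS since the previous visit. For all of these, section 3 says "Tests between groups will be made for the NR-RTX group and all of the other groups one at a time", using Mann-Whitney, Fisher or Mantel-Haenszel tests according to the type of variable. It names no covariate, stratification, matching or weighting, and does not say what follows if the groups differ at baseline.

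On size, SAP 1.4 says only "No power calculation was performed due to the lack of data from any similar study of RTX in GC non-responders".

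**The concern.** Patients reach NR-C by failing an entry criterion or by refusing, so there is no reason to expect them to match NR-RTX on characteristics that affect the course of CAS. If one group has had eye symptoms for longer, or smokes more, CAS can diverge without any effect of RTX. The bias could favour RTX or count against it.

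The plan collects the variables needed to reduce this problem but uses them only in stand-alone tests. Those tests leave the CAS comparison unchanged: a significant result triggers no action, and a non-significant one removes no imbalance. Followed exactly, the plan leaves measured confounding in its primary comparison.

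**Working it through.** The plan states no N, alpha, SD or effect size, so there is no figure of its own to reproduce. The check sizes the bias under stated assumptions.

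**Inputs from the documents**
- Non-randomised design and the source of NR-C: Protocol, Study design.
- Unadjusted two-group tests: SAP 3.
- No power calculation: SAP 1.4.
- 2000 new cases of Graves' disease a year in Sweden, 5-10% moderate-severe, 70-80% steroid responders: Protocol, Background.

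**Assumptions**
- Two-sided 5% level.
- 10-15 patients per group, with 20 and 30 shown for range.
- Baseline imbalance of 0.5-0.8 SD in one covariate.
- Correlation of that covariate with CAS of 0.3-0.5.
- CAS SD of 1.5 points.
- True RTX effect of zero.

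**1. Are small groups plausible?** Steroid non-responders per year in all of Sweden:
- low: 2000 × 0.05 × 0.20 = 20
- high: 2000 × 0.10 × 0.30 = 60

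The study recruits at one hospital. Small groups are likely, but the documents do not fix them.

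**2. Bias of the unadjusted comparison.** Bias = imbalance (SD) × correlation × CAS SD.
- low: 0.5 × 0.3 × 1.5 = 0.23 points
- high: 0.8 × 0.5 × 1.5 = 0.60 points

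Group size does not enter the formula, so recruiting more patients does not reduce the bias.

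**3. Simulation with no RTX effect** (10 and 20 per group, 2000 runs per setting):

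| Analysis | Bias (SD) | Bias (points, × 1.5) | Type I error |
|---|---|---|---|
| Unadjusted, all runs | 0.15 to 0.41 | 0.22 to 0.62 | 0.06 to 0.23 |
| Unadjusted, only runs with a non-significant background test | 0.10 to 0.28 | 0.15 to 0.42 | 0.05 to 0.08 |
| Adjusted for the covariate | -0.02 to +0.01 | about 0 | 0.04 to 0.06 |

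The 0.23 arises at 20 per group with an imbalance of 0.8 SD and a correlation of 0.5. The same setting at 10 per group gives 0.13. The bias is the same, but the larger groups make it easier to declare significant.

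**4. How often would the background test miss a large imbalance?** Mann-Whitney on a 0.8 SD difference in a continuous variable, share with p > 0.05:

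| Per group | Missed |
|---|---|
| 10 | about 65% |
| 15 | about 49% |
| 20 | about 34% |
| 30 | about 16% |

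The figures vary by two or three percentage points between simulation runs. For smoking in its three listed levels, treated as ordered and tested by Mantel-Haenszel (current smokers 20% v 50%, never-smokers 50% v 20%), the miss rates are 64%, 49%, 37% and 19%. At the smaller sizes the tests are a weak screen; at 30 per group they are a fair one for differences this large.

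**The case against.** The strongest reply is that the plan does not do what a reader might infer. Nothing in it says that p-values decide whether the groups are comparable, that p > 0.05 will be read as no difference, or that any CAS difference will then be credited to RTX. Whether background variables differ is a declared research question, against R-GC as well as NR-C, and a two-group test is an ordinary way to answer it. That stands. Preferring standardised differences for objective A is mostly a matter of reporting.

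Four further points also stand, in whole or in part:
- A reader might call the background tests underpowered as a fact. No N is stated, and at 30 per group a 0.8 SD imbalance is missed only about 16% of the time. Low power is an inference.
- Fisher's test on smokers v non-smokers would give higher miss rates, but the SAP lists three smoking levels and defines no such dichotomy, so those rates are not used here.
- One might add that many tests produce chance findings: 13 listed variables against two comparators give 1 - 0.95^26 = 74% for at least one p < 0.05, assuming independence and exact size. But the Protocol counts proptosis and diplopia as efficacy variables. The ten remaining variables against NR-C alone give 1 - 0.95^10 = 40%. Fisher's test is conservative in small groups, and the thyroid laboratory values are probably correlated. The argument adds little.
- Given a non-significant background test, the bias is smaller and type I error is only 0.05-0.08.

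None of this answers the central point, that the CAS comparison of two non-randomised groups has no adjustment at all.

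**Conclusion.** The concern holds for the CAS comparison, not for the use of tests in objective A. Measured confounding stays in NR-RTX v NR-C whatever the background tests show. Under the stated assumptions it amounts to about 0.2-0.6 CAS points, or about 0.15-0.4 where the background test is non-significant.

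These figures illustrate the scale; they do not predict this trial's bias. They depend on an assumed imbalance, correlation and CAS SD. The documents do not say that duration of eye symptoms or smoking predicts CAS, so choosing these two is itself an assumption. Nor should the figures be set against the 2-point change in CAS, which classifies individual patients at week 4 and is not a between-group target.

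The gap in the plan does not depend on any of these values. Because the remedy is cheap and uses variables already listed, the change should be made.

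**What to change.** In SAP section 3, prespecify that CAS in NR-RTX v NR-C is compared by one linear model, adjusted for duration of eye symptoms and current smoking (yes/no) alongside CAS at the switch, whatever the background tests show. State the reason for choosing these covariates. Keep the unadjusted Mann-Whitney test as a sensitivity analysis.

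Add standardised differences with 95% confidence intervals to the background table. State that confounding from the way NR-C is selected remains: two covariates cannot undo a control group formed by ineligibility or refusal.

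The cost is SAP wording, one regression and two extra degrees of freedom, or three if smoking keeps its three levels (1 + 2). At 10 per group the model leaves 20 - 5 = 15 residual degrees of freedom (intercept, group, CAS at the switch, duration, smoking), so the covariate list should stay this short. No new variable is needed, provided that duration and smoking can be retrieved for NR-C, which the Protocol's second aim already presumes.

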2.3.2 Secondary Variables

- Change of CAS between the observation timepoints and the baseline: comparison between the treatment groups
- Comparison of frequency of adverse events between NR-RTX and R-GC.
- TRAb antibodies

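### NR-RTX and R-GC are separated by their week 0-4 CAS change, before any RTX is given, so their later CAS comparison cannot show whether RTX lowers CAS

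*SAP*

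**What the plan says.** Under Study design, the Protocol starts every RTX-study patient on iv GC and evaluates the outcome after four weeks: "If the patients have improved their CAS score by ≥ 2 points, they are classified as responders to iv GC (R-GC"). The remainder are non-responders and are "switched to 1000 mg iv RTX in week 5 and 7, combined with a weekly oral dose of" MTX; they form NR-RTX. The third group, NR-C, consists of non-responders who stay on iv GC. It is drawn from patients who "do not meet inclusion/exclusion criteria for the RTX-study or declined participation".

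The Protocol's Objectives make NR-RTX versus NR-C the primary aim. R-GC enters in a second aim that compares background and efficacy variables. The Protocol's research question and SAP 1.1 (objective B) do not keep that separation: "Does RTX lower the CAS of the non-steroid responsive TAO-patients (NR-RTX), in comparison to NR-C, that continued with iv GC, and R-GC".

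SAP 2.3.1 lists two primary variables: change of CAS from the previous timepoint, and "CAS: comparison between the treatment groups at the different timepoints". SAP 2.3.2 adds "Change of CAS between the observation timepoints and the baseline: comparison between the treatment groups". SAP 3 tests NR-RTX against R-GC and NR-C one at a time, with Mann-Whitney for continuous variables. Neither document describes an adjustment for week-0 or week-4 CAS.

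**The concern.** The two groups are defined by an early value of the outcome on which they are later compared, and that value is fixed before RTX begins. They differ by definition in observed steroid response. Part of that difference is real and part is visit-to-visit error in CAS. Both parts carry into the later comparisons, and not in the same direction for each planned variable.

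At stake is how the R-GC half of objective B is read. A higher CAS or a smaller fall from baseline in NR-RTX could be taken as RTX failing, when it only restates the grouping. A larger fall from week 4 to week 12 in NR-RTX, on the first-listed primary variable, could be taken as RTX working, when it may be regression to the mean.

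**Working it through.** The plan gives no sample size, power, SD or effect size, so there is no figure of its own to reproduce. The check has three parts.

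**1. Week 0-4, no assumptions.** Every R-GC patient has a CAS fall of at least 2 and every NR-RTX patient a fall below 2, so the groups separate completely. A test of that change would be decided by the rule. With 4 v 4 patients (an arbitrary size), the exact two-sided p is 2/C(8,4) = 2/70 = 0.029. The SAP does not list its observation timepoints, so whether week 4 would be tested is open.

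**2. Direction of later bias if RTX has no effect.** Write observed CAS as true CAS plus an independent visit error of variance σ². Let δ be the true change from week 0 to 4 (variance h²) and γ the true change from week 4 to 12. Patients are sorted on D = δ + e4 − e0, and R-GC has the low values. The expected difference, NR-RTX minus R-GC, broadly follows the sign of each variable's covariance with D. This ignores rounding and the entry threshold, and takes true baseline as independent of δ:

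- change, baseline to week 12: h² + Cov(δ,γ) + σ²
- level, week 12: h² + Cov(δ,γ)
- step, week 4 to 12: Cov(δ,γ) − σ²
- step, week 12 to 18: 0, if true change after week 12 is unrelated to δ

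Unless Cov(δ,γ) is strongly negative, the first is positive, against NR-RTX. The second is near zero when patients do not truly differ in response. The third is negative, favouring NR-RTX, unless responders go on improving more than non-responders.

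Example of the reversal: 75% true responders fall 2.5 by week 4 and 3.5 by week 12; the others fall 0.5 and stay there. The gap in δ is 2.0 and the gap in γ is 1.0, so Cov(δ,γ) = 0.75 × 0.25 × 2.0 × 1.0 = 0.375. Subtracting σ² gives 0.375 − 0.09 = +0.285 at visit SD 0.3, 0.375 − 0.36 = +0.015 at 0.6, and 0.375 − 1.00 = −0.625 at 1.0.

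**3. Illustrative size.** From the documents: entry at CAS ≥4 on a 7-point scale, the 2-point rule, Mann-Whitney, and the Background's 70-80% response to GC (not tied there to the week-4 rule). Assumed: 30 or 50 patients; true baseline CAS N(5, 0.8); CAS rounded to 0-7; no true change after week 12. Continuous response: visit SD 0.6 or 1.0, between-patient SD of the fall 0, 0.5 or 1.0, then a common 0.5-point fall to week 12. Two classes: visit SD 0.3, 0.6 or 1.0, with falls to week 4 as in the example, then either diverging as there or a common further 0.5. There are 24 scenarios. Entries are the mean NR-RTX minus R-GC difference and the share of trials with p<0.05, with no RTX effect.

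| Measure | Continuous response | Two classes |
|---|---|---|
| Baseline to week 12 | +0.75 to +1.75 (35-100%) | +1.62 to +2.89 (76-100%) |
| Week-12 level | +0.16 to +1.37 (5-89%) | +1.04 to +2.82 (38-100%) |
| Week 4-12 step | −0.56 to −1.39 (29-84%) | common fall: about −0.1 to −1.06 (about 6-67%); diverging: about +0.84, +0.16, −0.61 at visit SD 0.3, 0.6, 1.0 |
| Week 12-18 step | −0.04 to +0.04 (4-6%) | near the nominal rate |

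The signs agree with part 2. A second set of assumptions (30 or 60 patients, baseline mean 4.8, mean fall 2.0, visit SD 0.5 or 0.8, continuous response) gives the same pattern: +0.68 to +1.94 (37-100%) from baseline to week 12, and −0.44 to −1.10 (22-87%) for the week 4-12 step.

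**The case against.** **R-GC is only a benchmark.** The Objectives place R-GC in a second aim of comparison. Asking whether RTX-treated non-responders come to resemble steroid responders is legitimate, and for that question the later level difference is the quantity of interest, not a bias. This stands for the second aim. It does not fit objective B or the research question, which set R-GC beside NR-C as a comparator for whether RTX lowers CAS.

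**The primary contrast is untouched.** A reader might infer that the whole efficacy analysis fails. The documents do not support that. NR-C is also a non-responder group, and NR-RTX versus NR-C avoids this flaw if NR-C meets the same week-4 rule. No passage says that NR-C patients, found through a registry, had a week-4 CAS recorded, so the condition is unconfirmed.

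**The bias is conservative.** Not reliably: it runs against NR-RTX on change from baseline and usually for it on the week 4-12 step.

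**Adjust instead.** Regression on group plus week-0 and week-4 CAS left a bias within 0.05 under continuous response, but +0.21 to +1.75 under two classes, so adjustment does not rescue a causal reading.

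**No p-values at all between these groups.** A reader might go this far. It exceeds the flaw: the Protocol plans the comparison, and steps after week 12 are about unbiased if both groups share the same true course. Labelling what the p-values mean is enough.

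**Relapse.** "Patients with relapse are randomized to either treatment with RTX and MTX" or to oral GC and MTX, so some R-GC patients later receive RTX. For DON, the Protocol says "they are excluded from the comparisons between groups after the occurrence of DON"; it states no such rule for relapse. A reader might infer a false RTX benefit of some definite size. No relapse rate is given, and a negative week 12-18 step appears if only R-GC is allowed to rebound, so no size is claimed.

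**Conclusion.** The concern holds for the R-GC part of objective B and the matching research question. A CAS difference between NR-RTX and R-GC, or its absence, cannot be attributed to RTX, because the groups were selected on early CAS change and the planned tests do nothing to correct it. The complete week 0-4 separation follows from the text alone.

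The later sizes rest on assumed sample sizes, SDs and trajectories; they show what can happen, not what will. Within those assumptions, change from baseline was biased against NR-RTX in every scenario. The bias in week-12 level ranged from almost none to severe. The week 4-12 step usually favoured NR-RTX but changed sign when classes diverged and visit error was small. The week 12-18 result near the nominal rate depends on independent visit errors and a shared true course.

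This should be fixed. It does not invalidate the trial: a relevant, though non-randomized, contrast remains.

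**What to change.** In SAP 1.1 (objective B), SAP 2.3 and 3, and the Protocol's research question:

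- Remove R-GC as a comparator for the RTX effect. Keep NR-RTX versus R-GC on CAS as the descriptive benchmark of the second aim.
- Do not test the week 0-4 change or the week-4 level between these two groups. State that any later CAS difference or p-value between them is not evidence of an RTX effect.
- Rest the RTX question on NR-RTX versus NR-C. Classify NR-C by the same rule (CAS improvement below 2 points at week 4) where a week-4 CAS is recorded, and measure change from week 4. State that this contrast is non-randomized, that NR-C patients were ineligible or declined, and that it assesses RTX plus MTX.
- In the R-GC display, mark values recorded after relapse randomization.

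The cost is wording in two documents; no treatment or visit changes. The price is that the R-GC contrast loses any causal reading, and NR-C patients without a week-4 CAS cannot be classified by the same rule, which may shrink that group. Differences in patient mix between NR-RTX and NR-C remain and need to be acknowledged.
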